10. Prior systemic radiation therapy (either IV, intrahepatic or oral) completed at least 4 weeks prior to study drug administration; **(for ipilimumab combination please see supplement FEC exclusion criteria).**
11. Prior focal radiotherapy completed at least 2 weeks prior to study drug administration.
12. Prior major treatment-related surgery completed at least 4 weeks prior to study drug administration.
13. No prior primary or metastatic brain or meningeal tumors unless clinically and radiographically stable as well as off steroid therapy for at least 2 months.
14. Life expectancy ≥ 8 weeks; **(for ipilimumab combination please see supplement FEC inclusion criteria).**
15. A female participant is eligible to participate if she is not pregnant, not breastfeeding, and at least one of the following conditions applies:
 - a. Not a woman of childbearing potential (WOCBP)
 - b. A WOCBP subject who may become pregnant or who are sexually active with a partner and who could become pregnant agrees to use an effective form of barrier contraception during the study and for at least 180 days in monotherapy; **(for pembrolizumab and ipilimumab combinations please see supplements DEC/DEC2 and FEC for pregnancy criteria).** (Male subjects must agree to use contraception and refrain from sperm donation during the study for 180 days after administration of study drug.)
16. Have adequate organ function as defined by the below screening laboratory values that must meet the following criteria:
 - a. WBC $\geq 2000/\mu\text{L}$ ($\geq 2 \times 10^9/\text{L}$).
 - b. Neutrophils $\geq 1000/\mu\text{L}$ ($\geq 1 \times 10^9/\text{L}$); **(for pembrolizumab and ipilimumab combinations please see supplements DEC/DEC2 and FEC for neutrophil criteria).**
 - c. **For subjects with planned superficial only injections:** PT, PTT/aPTT, and INR $\leq 1.5 \times \text{ULN}$, Platelets $\geq 70 \times 10^3/\mu\text{L}$ ($\geq 70 \times 10^9/\text{L}$), Hemoglobin $\geq 8 \text{ g/dL}$
 - d. Creatinine within the institution's laboratory upper limit of normal or calculated creatinine clearance $> 50 \text{ ml/min}$; **(for pembrolizumab combination please see supplements DEC/DEC2 for creatine criteria).**
 - e. ALT (SGOT)/AST (SGPT) $\leq 2.5 \times \text{ULN}$ without, and $\leq 5 \times \text{ULN}$ with hepatic metastases.

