13.1. Definitions

An adverse event is any undesirable sign, symptom, clinically significant laboratory abnormality, or medical condition occurring after starting study treatment, even if the event is not considered to be study drug-related. Each adverse event is to be reported on an Adverse Event CRF page. Adverse events are graded using the Cancer Therapy Evaluation Program (CTEP) CTCAE, Version 4.03. If CTCAE grading does not exist for an adverse event, the severity of mild (1), moderate (2), severe (3), life-threatening (4), and death related to an adverse event (5) will be used. Information about all adverse events, whether volunteered by the subject, discovered by Investigator questioning, or detected through physical examination, laboratory testing, or other means, will be collected, and recorded on the Adverse Event CRF page and followed as appropriate. Adverse event monitoring should be continued until adverse event resolution/stabilization (whichever is later).

Medical conditions/diseases present before the injection of study drug are only considered adverse events if they worsen after receiving any study drug. Clinical events occurring before the administration of study drug but after signing the ICF and providing HIPAA authorization are to be recorded on the Medical History/Current Medical Conditions CRF page. All laboratory values are to be reviewed by the Investigator and abnormal values will be graded according to CTCAE Version 4.03 and reported in the study report.

A laboratory abnormality is considered an adverse event if it results in:

- discontinuation from study drug,
- necessitates therapeutic medical intervention,
- if the Investigator assesses the abnormality as an adverse event, or
- any laboratory test that is clinically significant or meets the definition of a SAE

It is expected that wherever possible, the clinical, rather than the laboratory term would be used by the reporting investigator (e.g., anemia versus low hemoglobin value). These adverse events will be recorded on the Adverse Events CRF page and will include all signs, symptoms, or diagnosis associated with them.

As far as possible, each adverse event will also be described by:

1. Description
2. Duration (start and end dates)
3. CTCAE Grade 1 through 5 or severity if CTCAE is not available
4. Relationship to the study drug - related or not related
5. Relationship to the dosing procedure – related or not related
6. Action(s) taken with study drug

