Clinical laboratory values will be summarized in SI units. Severity grades will be programmatically calculated using standard American Medical Association's (AMA) laboratory normal ranges [AMA Manual of Style, AMA 2009] and the quantitative NCI CTCAE 4.03 criteria (when available for a specific laboratory abnormality). Laboratory values considered to be normal by CTCAE criteria, meaning they do not qualify as Grade 1-4, will be assigned a severity grade of 0.

Summary statistics of numerical laboratory test results and changes of test results from baseline will be reported for hematology, coagulation, serum chemistry, and urinalysis at each scheduled time point. For values with categorical results, the frequency and percentage of each result category will be tabulated at each scheduled time point. Shift tables will also be included reporting change from baseline category (low, normal, high) to post-dose category (low, normal, high). Abnormal laboratory values that lead to a change in subject management or that are considered to be of clinical significance will be reported as an adverse event (serious adverse event if relevant) and summarized by SOC/PT and according to severity in the appropriate AE tables. Clinical significance will be determined by the Principal Investigator at each site.

Pregnancy test results will be displayed in a listing.

ECOG Performance Status

ECOG performance status will be summarized using descriptive statistics. ECOG performance status per subject during the trial will also be listed.

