10.2. Clinical Laboratory Evaluations

Clinical laboratory values will be summarized in SI units. Severity grades will be programmatically calculated using standard American Medical Association's (AMA) laboratory normal ranges [AMA Manual of Style, AMA 2009] and the quantitative NCI CTCAE 4.03 criteria (when available for a specific laboratory abnormality). Laboratory values considered to be normal by CTCAE criteria, meaning they do not qualify as Grade 1 - 4, will be assigned a severity grade of 0. For laboratory tests without any CTCAE criteria, toxicity grades will be recorded as 99.

Summary statistics of numerical laboratory test results and changes of test results from baseline will be reported by treatment for hematology, coagulation, serum chemistry, and urinalysis at each scheduled time point. For values with categorical results, the frequency and percentage of each result category will be tabulated at each scheduled time point by treatment. Shift tables will also be included reporting change from baseline category (low, normal, high) to post-dose category (low, normal, high) for cohorts and overall. Abnormal laboratory values that lead to a change in subject management or that are considered to be of clinical significance will be reported as an adverse event (serious adverse event if relevant) and summarized by SOC/PT and according to severity in the appropriate AE tables. Clinical significance will be determined by the Principal Investigator at each site.

Individual test result records, including repeat assessments, and comments for hematology, coagulation, serum chemistry, and urinalysis will be displayed in listings. Laboratory values outside normal limits will be identified with flags for high, low, and normal limits in the listings. Pregnancy test results will be displayed in a listing.

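### SAP 10.2 derives CTCAE grades for laboratory values but names no summary that uses them, and its low/normal/high shift table cannot show same-direction worsening from an abnormal baseline

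*SAP*

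**What the plan says.** SAP 10.2 sets out the grading in three steps. First, "Severity grades will be programmatically calculated", using AMA reference ranges and "the quantitative NCI CTCAE 4.03 criteria (when available for a specific laboratory abnormality"). Second, values that are normal by those criteria, meaning "they do not qualify as Grade 1 - 4, will be assigned a severity grade of 0". Third, "For laboratory tests without any CTCAE criteria, toxicity grades will be recorded as 99".

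The section then lists its outputs for numeric tests:
- summary statistics of values and changes from baseline at scheduled time points, by treatment;
- shift tables "reporting change from baseline category (low, normal, high) to post-dose category (low, normal, high"), for cohorts and overall;
- listings of individual results, with high, low and normal flags.

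Values that alter a subject's management, or that the site investigator considers clinically significant, also go to the adverse event tables.

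Protocol 14.3.5 (Clinical Laboratory Tests) has the same layout: "Shift tables will also be included reporting change from baseline category (low, normal, high) to post-dose category (low, normal, high"). Protocol 13.1 goes further and says that "abnormal values will be graded according to CTCAE Version 4.03 and reported in the study report".

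**The concern.** The SAP derives a five-level severity scale and then summarises laboratory change on a three-level scale that carries no severity. None of the outputs named in SAP 10.2 tabulates the derived grades, so the commitment in Protocol 13.1 has a derivation behind it but no stated output.

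This matters in this trial for three reasons. Safety is the primary objective. The SAP synopsis names renal and blood toxicity as known for the two active agents. The protocol itself also works by laboratory grade: new Grade 3 or higher abnormalities must be assessed for risk to continued dosing (12.1.3), and several items in the discontinuation list in 8.12 are defined by grade. A reader of the study report would expect to see how many subjects reached those grades by measured value. The SAP text does not require that count.

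**Working it through.** The plan states no figure to reproduce, and no sample size or error rate is involved. The check is whether an abnormal baseline can occur, and what the table then does with it.

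**Step 1: can a subject enter with an abnormal value?** From Protocol 6.1:

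| Test | Entry limit | Scope |
|---|---|---|
| ALT/AST | up to 2.5 x ULN; 5 x ULN with hepatic metastases | no deferral to a supplement stated |
| Bilirubin | up to 2 x ULN | defers to supplements for both combinations |
| Creatinine | within ULN, or clearance above 50 mL/min | defers to supplement for pembrolizumab |
| Neutrophils | from 1000/µL | defers to supplements for both combinations |
| Platelets | from 70 x 10^9/L superficial only; from 100,000/µL deep | by injection type |
| Hemoglobin | from 8 g/dL superficial only; from 9 g/dL deep | by injection type |

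The ALT/AST row is enough. Its limit is a multiple of ULN, so a 'high' baseline is eligible whatever reference range applies. For counts and hemoglobin, a 'low' baseline assumes that the lower limit of normal lies above the entry limit. The documents do not print the ranges.

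**Step 2: where does worsening fall?** Write b for the baseline value and d for a later rise, both in multiples of ULN. The category is 'high' when the value exceeds 1. If b > 1 and d > 0, then b + d > 1, so the post-dose category is 'high' for every d.

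| Baseline | Post-dose | Shift cell |
|---|---|---|
| ALT 2 x ULN | unchanged, 2 x ULN | high to high |
| ALT 2 x ULN | any higher value | high to high |
| ALT normal | just above ULN | normal to high |
| ALT normal | severe rise | normal to high |

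Rows 1 and 2 cannot be told apart, and neither can rows 3 and 4. The low side is symmetrical. SAP 10.2 does not say which post-dose value is categorised, but taking the worst one would not change these cells. A move across the normal range, such as high to low, would show.

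**Step 3: what would the grades show?** Low/normal/high gives 3 x 3 = 9 cells. Grades 0-4 give 5 x 5 = 25 cells per direction, and any rise in grade leaves the diagonal.

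**Step 4: do the other named outputs count laboratory Grade 3-4 values?**
- Adverse event tables (SAP 10.1) give severity, but only for abnormalities that became adverse events.
- By-visit statistics (SAP 7.1) give the minimum and maximum, which show that an extreme value occurred but not how many subjects had one.
- Listings show every value, with high/low/normal flags. The text mentions no grade flag and no count.
- SAP 7.1 keeps unscheduled measurements out of summary tables, so a severe value found between visits reaches only the listings unless it is also an adverse event.

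None of the four provides the count.

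**The case against.** The strongest reply is that severe laboratory toxicity is captured elsewhere. Much of this stands. Protocol 13.1 makes an abnormality an adverse event if it leads to discontinuation or needs therapeutic intervention, as well as when the investigator judges it to be one. Protocol 8.12 lists laboratory findings that end treatment if unresolved before the next dose, including Grade 3 or higher liver enzymes and stated platelet and creatinine limits. SAP 10.1 counts an event present at baseline that worsens as treatment-emergent, and tabulates events by maximum severity. For subjects still on treatment, most severe laboratory changes should therefore appear in the adverse event tables.

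It also stands that the SAP follows the protocol's own table, and that layouts sit in a companion shells document not among the documents reviewed. A grade table may exist there. Deriving grades with codes 0 and 99 suggests that some output was intended.

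The reply does not supply a laboratory summary independent of adverse event reporting. Programmed grades have value as a check because they do not depend on whether a value was acted on or reported.

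A reader might infer that severe laboratory toxicity would vanish from the report, or that the primary safety result is compromised. The documents do not support either. The routes above remain, and the primary measure in Protocol 4.2 and SAP 10 is the rate of attributed Grade 3 or higher adverse events, which does not draw on the shift table.

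**Conclusion.** The gap is real and moderate. SAP 10.2 derives grades without naming a summary for them, and the one shift table it specifies cannot show same-direction worsening from an abnormal baseline or separate mild from severe change from a normal one. The loss is confined to the laboratory summaries.

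The number of subjects affected cannot be stated, because the documents give no distribution of baseline laboratory values. A share such as 30-50% entering with an abnormal value would be an assumption only, and it would not say how many of those subjects worsen severely. Nor can the main-protocol limits for neutrophils and bilirubin be carried to the combination cohorts, or the creatinine limit to the pembrolizumab cohorts, since those criteria sit in supplement text not available here.

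The conclusion rests on the ALT/AST entry limits, the three-category layout and the wording of SAP 10.2. It needs no CTCAE cut-offs, which the documents do not print. It would narrow to a wording point if the shells already contain a grade table.

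**What to change.** Keep the low/normal/high table, which the protocol specifies and which still serves tests coded 99. Add to SAP 10.2:

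1. A shift table of baseline CTCAE grade (0-4) to worst post-baseline grade, by treatment as defined in SAP 7.1 and by direction of abnormality (hypo/hyper), for every analyte with CTCAE criteria.
2. The number and percentage of subjects reaching Grade 3 or higher for each of those analytes.
3. A statement that unscheduled measurements count toward the worst grade, as an explicit exception to the SAP 7.1 rule. Without it, values measured between visits would drop out of the new table.

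If the shells already hold such a table, SAP 10.2 needs only to name it and add the exception for unscheduled values.

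The cost is a modest amount of programming and some extra output pages. The grades are already to be derived, so no new data are needed.

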10.3. Vital Signs

Vital sign measurements and change from baseline will be summarized by cohort, tumor type and study visit using descriptive statistics. Vital signs include weight, systolic blood pressure (SBP), diastolic blood pressure (DBP), body mass index (BMI, derived), heart rate, oxygen saturation, and temperature. Individual vital sign measurements will be listed.

10.4. ECGs

Summary statistics of ECG overall interpretation will be displayed by treatment and study visit. Per subject ECG test results will be listed.

Abnormal clinically significant ECG findings on or after informed consent will be recorded as an adverse event and displayed with AEs.

10.5. Physical Examination

Abnormal PE findings with onset prior to first dose of study drug will be recorded as medical history. Any abnormal or clinically significant findings on or after dosing will be recorded as an adverse event. Clinical significance will be determined by the Principal Investigator at each site.

Individual medical/surgical history will be listed by subject. Individual abnormal or clinically significant PE findings after dosing will be recorded as an adverse event and listed separately with AEs.

11. CLINICAL PHARMACOLOGY ANALYSES

Not Applicable.

12. OTHER ANALYSES

12.1. Pharmacokinetic Analysis

PK analysis is detailed in the PK manual. Pharmacokinetic are out of the scope of this analysis plan and will be summarized separately.

12.2. Exploratory Biomarkers of Immune Response

Summary statistics for immune function and other exploratory markers, such as but not limited to flow cytometry outcomes, cytokines, quantitative immunoglobulins, quantitative inflammatory infiltrates, T-cell repertoire and their changes (or percent changes) from baseline will be tabulated by cycle visit and dose to assess pharmacodynamic effects. In addition, the time course of biomarker outcomes will be investigated graphically, by summary plots (i.e., box plots) or individual subject plots over time. Possible associations between changes in biomarker measures of interest and pharmacokinetic exposure will be explored.

Measures from markers based on optional samples, e.g., tumor-based markers may be similarly presented, depending on data availability. Additional information can be found in the Biomarker Manual.

Biomarker analyses are out of the scope of this analysis plan and will be summarized separately.

12.3. Pharmacodynamic Analyses

Pharmacodynamic analyses are out of the scope of this analysis plan and will be summarized separately.

13. CHANGES IN THE STATISTICAL METHODS FROM THOSE STATED IN THE PROTOCOL

None.

15. TABLES, FIGURES, LISTINGS

Tables, listings and figures will be generated according to the companion document which details the layout of the output. Minor style deviation from specification defined in the shell document in the final production is permissible.

APPENDIX 1.

The following information provides additional programming instructions to define important variables that are not available in the main SAP text.

1. TOTAL TUMOR BURDEN (TTB)

Step 1: If all 3 dimensions are reported, volume = (longest*shortest*depth*0.63)

Step 2: If not all 3 dimensions are reported and longest diameter is reported, volume calculation is based on the longest diameter measurement.

1. If $. < \text{longest} < 1.5 \text{ cm}$, volume = 1 cm^3
2. If $1.5 \leq \text{longest} \leq 4 \text{ cm}$, volume = $\text{longest}^3/2$
3. If $4 < \text{longest} < 9 \text{ cm}$, volume = $\text{longest}^3/3$
4. If $\text{longest} \geq 9 \text{ cm}$, volume = $\text{longest}^3/4$
5. If shortest is only measurement reported, Diameter = shortest and follow step 2 tasks 1 to 4 for volume calculations

Step 3: Sum all calculated volume values across target and bystander tumors.

2. % DOSED TTB

Step 1. Calculate TTB of all of a patient's bystander and target tumors reported in the database using the TTB formulas above.

Step 2. Calculate patient's cumulative dose of INT230-6

Step 3. Calculate % Dosed TTB as (cumulative dose / Patient TTB) * 100.

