3.9. Starting Dose Selection Method and Dose Escalation

FDA agreed to a protocol that used 1/10 of the STD₁₀ to set the starting dose. The STD₁₀ in the rat pivotal study was approximately 7.5 mL/kg¹. As a result, 1/10 of the rat STD₁₀ is 0.75 mL/kg, which equates on a body surface area basis to a human dose of 7.3 mL/60 kg subject². Therefore, Sponsor proposed that the maximum permissible starting dose for the first-in-human (FIH) trial be up to 5.0 mL per subject. The target dose per tumor of INT230-6 for the first cohort was 0.25 mL per cm³ of the tumor's volume (i.e., 1:4 loading dose). This drug dose volume to tumor volume ratio has consistently shown to saturate large tumors in pharmacology testing and resulted in anti-tumor activity in multiple preclinical models. An injected or to-be-injected tumor's volume was determined using the ellipsoid calculation method (██████████) using the imaging technique available at the site (e.g., CT, ultrasound, or MRI). In Amendment 6, Sponsor is implementing a method to set INT230-6 dose for an individual tumor based on longest diameter.

¹ The actual value for 7.5 mL/kg IV was 12.9%.

² $(0.75 \div 6.2 = 0.121 \text{ mL/kg, or } 7.3 \text{ mL for a } 60 \text{ kg person } (60 \times 0.121))$

The total injected volume and the maximum per any one tumor was escalated in the phase 1 portion of the study. As noted above, the toxicology program showed that INT230-6 administered IV resulted in no new toxicities. Only events expected for either vinblastine or cisplatin were observed. Please refer to the IB for further information.

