At baseline, lesions are classified as measurable or nonmeasurable per either RECIST 1.1 guidelines, depending on the cohort. Baseline measurable lesions are further classified as target (injected) or bystander (non-injected), while non-measurable lesions are classified as non-target (non-target lesions are not eligible for injection). A sum of diameters (SOD) (longest for extranodal lesions and shortest for lymph nodes) will be calculated for all target lesions. Tumor volume (for target tumors with three dimensions) will also be calculated using the modified

ellipsoid method or by longest diameter if specified in an particular protocol amendment. Bystander lesions will be recategorized as target lesions once injected, but target lesions will always remain target lesions.

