3. INJECTED TUMOR RESPONSE RATE (ITR)

At a given visit, assess whether each injected tumor has achieved a PR or CR per RECIST 1.1. Count the total number of target (injected) tumors that achieve a PR or CR and divide by the total number of target tumors at that visit. This is the ITR. A PR is defined as a change $\geq 30\%$ in tumor volume, a CR is defined as having no visible tumor.

Note: for re-baselining retreated subjects that switch to a new cohort, the last assessment prior to the first retreatment is used as the baseline reference for determining PR.

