-Upon being treated as Repeat Assessment 1, subject is now considered for ITR. The last bystander measurement is used as baseline for ITR calculation on the first treatment course.

-Patient is retreated in the 3rd to last row (C2D0 retreatment). ITR calculation is restarted for new cohort, using the last record from the EC cohort as baseline.

Dosed TTb

Consider the following hypothetical patient's baseline tumor burden for calculation of Dosed TTb.

USUBJID	Tumor Class	TRLNkID	Longest Diameter	Shortest Diameter	Depth	(LD*SD*Depth*0.63)
1001	Target	T-1	4	3	3	22.68
1001	Target	T-2	2	1	1.5	1.89
1001	Bystander	BY-11	2	1	1	1.26
1001	Bystander	BY-12	1.5	1.2	1	1.134

To find TTb, we would simply add the tumors' individual LD*SD*D*0.63 calculations together: $22.68+1.89+1.26+1.134 = 26.964$

To calculate % dosed TTb , we add up the total dose received by the patient and divide it by the patient's TTb. For example, if this patient received a total of 20 ml in T-1 and 1 ml in T-2 of INT230-6, the % dosed TTb would be $(20\text{mL} + 2\text{ mL}) / (26.964\text{ cc}) * 100 = \sim 81.5\%$

Note that this example TTb calculation had all 3 measurements available (LD, SD, Depth) and so just uses Step 1 from the formula for TTb. Had less measurements been available, we would proceed to Step 2, calculate TTb as indicated, and sum them together in the same way.

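### SAP Appendix 1 scores injected-tumor PR on volume without naming the formula, and its only volume rule is unreliable for judging whether a tumor has shrunk

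*SAP*

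**What the plan says.** SAP Appendix 1 item 3 assesses every injected tumor at each visit: "A PR is defined as a change $\geq 30\%$ in tumor volume". It gives neither a formula nor a direction of change, and it also refers to RECIST 1.1. Item 4 applies the same method to bystander tumors.

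The only volume formulas in the Appendix are in item 1, under TTB. Step 1 is 0.63 × longest × shortest × depth when all three dimensions are reported. Step 2 covers the rest: "If not all 3 dimensions are reported and longest diameter is reported, volume calculation is based on the longest diameter measurement". It assigns 1 cm³ below 1.5 cm, LD³/2 from 1.5 to 4 cm, LD³/3 above 4 and below 9 cm, and LD³/4 from 9 cm. The worked TTB example at the end of the Appendix confirms the fallback: "Had less measurements been available, we would proceed to Step 2, calculate TTb as indicated, and sum them together in the same way".

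SAP Section 9 words the choice differently. Target tumors with three dimensions get volume by the modified "ellipsoid method or by longest diameter if specified in an particular protocol amendment". There the LD alternative is triggered by an amendment, not by a missing dimension.

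Neither document requires the formula used for a tumor at baseline to be used again at follow-up.

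**The concern.** A programmer who needs a tumor volume for item 3 will find only item 1 in the Appendix. The two formulas there are not interchangeable. If a tumor is measured in different ways at two visits, part or all of its apparent change comes from the formula.

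The LD steps have a second problem: they jump at their cut points and are flat below 1.5 cm. That may be tolerable for a rough total burden, but not for judging a 30% change in one tumor.

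Injected tumor response is a secondary endpoint for DEC, DEC2 and FEC in SAP Table 2. SAP Section 9 says efficacy will rest mainly on individual tumors. A PR rule that can give a wrong answer in either direction therefore needs repair.

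**Working it through.** **Inputs.** Formulas: SAP Appendix 1 item 1. PR threshold: item 3, 30%, read as a decrease. Tumors: the hypothetical patient in the Dosed TTb example.

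**Reproducing the SAP's figure.** Step 1 gives 22.68 + 1.89 + 1.26 + 1.134 = 26.964 cc, as stated.

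**Same tumors, both formulas, no change in size.** All four have LD between 1.5 and 4 cm, so Step 2 is LD³/2.

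| Tumor | L × S × D (cm) | Step 1 (cc) | Step 2 (cc) | LD only, then 3 dimensions | 3 dimensions, then LD only |
|---|---|---|---|---|---|
| T-1 (target) | 4 × 3 × 3 | 22.68 | 32.00 | −29.1% | +41.1% |
| T-2 (target) | 2 × 1 × 1.5 | 1.89 | 4.00 | −52.8% | +111.6% |
| BY-11 (bystander) | 2 × 1 × 1 | 1.26 | 4.00 | −68.5% | +217.5% |
| BY-12 (bystander) | 1.5 × 1.2 × 1 | 1.134 | 1.69 | −32.8% | +48.8% |

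Of the two injected tumors, T-2 reads as PR with no change when LD alone is recorded at baseline. T-1 just misses.

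**A true response, reverse order.** Shrink every dimension by 20%. True volume change is 0.8³ − 1 = −48.8%, a PR. With three dimensions at baseline and LD only later:
- T-1: LD 3.2 cm, 3.2³/2 = 16.38 cc against 22.68, or −27.8%. Not PR.
- T-2: LD 1.6 cm, 1.6³/2 = 2.05 cc against 1.89, or +8.4%. Not PR.

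**LD at both visits, no switch of formula.**
- 1.50 to 1.49 cm: 1.6875 to 1.00 cc, −41%. PR on a 0.1 mm change.
- 4.00 to 4.01 cm: 32.0 to 4.01³/3 = 21.5 cc, −33%. PR on growth.
- 1.4 to 0.7 cm: 1.00 to 1.00 cc, 0%. With proportional shrinkage the true change is 0.5³ − 1 = −87.5%. Tumors are eligible from 1.0 cm (Protocol Section 6.1).

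**One measure at both visits.** With Step 1 volume at both, or LD at both, an unchanged tumor shows 0%.

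**TTB.** Step 2 for all four tumors gives 32 + 4 + 4 + 1.6875 = 41.69 cc, 55% above 26.96. The 40% dosed-burden cut then falls at 0.4 × 41.69 = 16.7 mL instead of 0.4 × 26.96 = 10.8 mL. The example patient stays above 40% either way: the 22 mL used in the SAP's sum is 81.6% or 52.8%. (The SAP's text gives 20 mL and 1 mL; 21 mL is 77.9% or 50.4%.)

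**The case against.** **The SAP does not say that the formula is chosen visit by visit.** This stands. Item 1 is written for TTB, which the SAP uses as a baseline quantity. Item 2 invokes the TTB formulas expressly and item 3 does not. A reader might infer a prescribed visit-by-visit switch. What the text supports is narrower: the response formula is undefined, the only one in the Appendix is unsuitable, and Section 9 has a different trigger.

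**Three of the four example tumors would become PR.** A reader might draw this from the table, but it needs LD only at baseline and three dimensions later. The SAP's example has all three at baseline, and from there a fall back to LD makes all four appear to grow. Two of the three are also bystanders, and SAP Section 9.1 places the bystander response analysis outside the SAP.

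**Amendment 6 makes the formula track cohort and calendar time.** Not established. Protocol Section 3.9 says "In Amendment 6, Sponsor is implementing a method to set INT230-6 dose for an individual tumor based on longest diameter", which concerns dosing. Nothing says that sites stopped recording three dimensions, and SAP Section 9.1 plans to list all of them.

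**The formulas may agree better in practice.** Protocol Section 5.2 reports consistent proportions across more than 200 tumors. A 5 cm tumor with T-1's proportions (5 × 3.75 × 3.75 cm) is 44.3 cc by Step 1 and 125/3 = 41.7 cc by Step 2, a 6% gap. But constant shape cannot make the formulas agree everywhere, because the Step 2 divisor changes with size. For T-1's shape, S × D/L² = 9/16, and Step 1 divided by Step 2 is 0.63 × 9/16 × divisor: 0.71, 1.06 and 1.42 for divisors 2, 3 and 4.

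**The main efficacy results are untouched.** This stands. DCR counts CR, PR and SD alike, and progression is clinical or radiographic deterioration, so calling SD a PR changes neither DCR nor PFS, and OS counts deaths.

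**Conclusion.** The point holds as a defect in the definition of tumor-level PR. The formula is not named, two places in the SAP give different triggers, and the only detailed rule gives wrong answers at its own cut points even when a tumor is measured in the same way throughout.

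For individual tumors the errors are large against a 30% threshold: −53% with no change in size, +8% after a true 49% loss, −33% on 0.1 mm of growth. The switching results assume that item 1 is used for response and that the recorded dimensions differ between visits. The cut-point results need only item 1 and LD-only records. Since the documents do not give the frequency of missing dimensions, no effect on the ITR can be stated. The consequence is confined to tumor-level response; the 40% dosed-burden grouping is a separate, smaller question about TTB.

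**What to change.** In Appendix 1 items 3 and 4:
- State that PR is a decrease.
- Require the same measure at baseline and follow-up for each tumor: Step 1 volume only when all three dimensions exist at both visits, otherwise LD against LD with at least a 30% decrease.
- Never score PR from a Step 2 volume.

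Reconcile SAP Section 9 with Appendix 1 items 1 and 3, so that one sentence says which volume is used for response and when.

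For TTB, keep the planned rule. As a sensitivity analysis, report how many subjects change 40% category when LD volumes are used for all tumors. Forcing one rule on all of a subject's tumors in the main analysis would discard recorded measurements.

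The cost is SAP wording and a few lines of code before database lock, with no new data. The downside is that some tumors are scored on diameter instead of volume. That is a stricter test: with proportional shrinkage, a 30% fall in LD is a 1 − 0.7³ = 66% fall in volume. The ITR table should therefore show how many tumors were scored each way.
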